Incidence of device-related or insertion/removal procedure-related serious adverse events over the operating life of the Sensor	0	0 (0.0%)
Incidence of insertion/removal procedure or device-related adverse events in the clinic and during home use	12	11 (15.5%)
Incidence of all adverse events in the clinic and during home use	35	24 (26.6%)
Incidence of hospitalizations due to hypoglycemia, hyperglycemia, or ketoacidosis occurring during home use	0	0 (0.0%)
Incidence of reported hypoglycemic and hyperglycemic events occurring during home use	2	2 (2.8%)

Table 4B. Other Safety Endpoint for Subjects between 18 and 20 Years Old (Sample Data)

Type of Incidence	Number of Incidents	Number (%) of Subjects with Incidents
Incidence of device-related or insertion/removal procedure-related serious adverse events over the operating life of the Sensor	0	0 (0.0%)
Incidence of insertion/removal procedure or device-related adverse events in the clinic and during home use	12	11 (15.5%)
Incidence of all adverse events in the clinic and during home use	35	24 (26.6%)
Incidence of hospitalizations due to hypoglycemia, hyperglycemia, or ketoacidosis occurring during home use	0	0 (0.0%)
Incidence of reported hypoglycemic and hyperglycemic events occurring during home use	2	2 (2.8%)

Table 4C. Safety Endpoint for Subjects between 21 and 44 Years Old (Sample Data)

Type of Incidence	Number of Incidents	Number (%) of Subjects with Incidents
Incidence of device-related or insertion/removal procedure-related serious adverse events over the operating life of the Sensor	0	0 (0.0%)
Incidence of insertion/removal procedure or device-related adverse events in the clinic and during home use	12	11 (15.5%)
Incidence of all adverse events in the clinic and during home use	35	24 (26.6%)

Incidence of hospitalizations due to hypoglycemia, hyperglycemia, or ketoacidosis occurring during home use	0	0 (0.0%)
Incidence of reported hypoglycemic and hyperglycemic events occurring during home use	2	2 (2.8%)

Table 4D. Safety Endpoint for Subjects between 45 and 65 Years Old (Sample Data)

Type of Incidence	Number of Incidents	Number (%) of Subjects with Incidents
Incidence of device-related or insertion/removal procedure-related serious adverse events over the operating life of the Sensor	0	0 (0.0%)
Incidence of insertion/removal procedure or device-related adverse events in the clinic and during home use	12	11 (15.5%)
Incidence of all adverse events in the clinic and during home use	35	24 (26.6%)

YSI Glucose Ranges (mg/dL)	Number of Paired CGM-YSI	Mean Relative Difference (%)	Median Relative Difference (%)	Mean Absolute Relative Difference (%)	Median Absolute Relative Difference (%)
Overall					
<40*					
40-60*					
61-80*					
81-180					
181-300					
301-350					
351-400					
>400					

*For YSI ≤80 mg/dl, the differences in mg/dl are included instead of percent difference (%).

Table 6B. CGM System Difference to YSI within CGM System Glucose Range (Sample Table)

CGM System Glucose Ranges (mg/dL)	Number of Paired CGM-YSI	Mean Relative Difference (%)	Median Relative Difference (%)	Mean Absolute Relative Difference (%)	Median Absolute Relative Difference (%)
Overall					
40-60*					
61-80*					
81-180					
181-300					
301-350					
351-400					

*For CGM ≤ 80 mg/dL, the differences in mg/dL are included instead of percent difference (%).

Table 6C. CGM System Agreement to Reference within YSI Glucose Ranges (Sample Table)

YSI Glucose Range (mg/dL)	Number of Paired CGM and YSI Reference	Percent of CGM System Readings Within				
		Percent 15/15% of Reference	Percent 20/20% of Reference	Percent 30/30% of Reference	Percent 40/40% of Reference	Percent Greater than 40/40% of Reference
Overall						
< 40						
40 - 60						
61 - 80						
81 - 180						
181 - 300						
301 - 350						

YSI Glucose Range (mg/dL)	Number of Paired CGM and YSI Reference	Percent of CGM System Readings Within				
		Percent 15/15% of Reference	Percent 20/20% of Reference	Percent 30/30% of Reference	Percent 40/40% of Reference	Percent Greater than 40/40% of Reference
351 - 400						
> 400						

Table 6D. CGM System Agreement to Reference within CGM System Glucose Ranges (Sample Table)

CGM System Glucose Range (mg/dL)	Number of Paired CGM and YSI Reference	Percent of CGM System Readings Within				
		Percent 15/15% of Reference	Percent 20/20% of Reference	Percent 30/30% of Reference	Percent 40/40% of Reference	Percent Greater than 40/40% of Reference
Overall						
40 - 60						
61 - 80						
81 - 180						
181 - 300						
301 - 350						
351 - 400						

Table 6E. CGM System Difference to YSI within Glycemic Ranges (Sample Table)

YSI Glucose Ranges (mg/dL)	Number of Paired CGM-YSI	Mean Absolute Difference (mg/dL)	Mean Absolute Relative Difference (%)
Overall			
<70			
70-180			
>180			

Table 6F. CGM System Agreement to Reference within Glycemic Ranges (Sample Table)

YSI Glucose Range (mg/dL)	Number of Paired CGM and YSI Reference	Percent of CGM System Readings Within				
		Percent 15/15% of Reference	Percent 20/20% of Reference	Percent 30/30% of Reference	Percent 40/40% of Reference	Percent Greater than 40/40% of Reference
Overall						
< 70						
70-180						
>180						

Table 7A. Concurrence of CGM System Readings and YSI Values within YSI Glucose Ranges (Sample Table)

YSI (mg/dL)	Number of Paired CGM-YSI (n)	Percent of Matched Pairs in Each CGM System Glucose Range for Each YSI Glucose Range								
		CGM (mg/dL)								
<40										
40-60										
61-80										
81-120										
121-160										
161-200										
201-250										
251-300										
301-350										
351-400										
>400										

Table 7B. Concurrence of CGM System Readings and YSI Values within CGM System Ranges (Sample Table)

CGM (mg/dL)	Number of Paired CGM-YSI (n)	Percent of Matched Pairs in Each YSI Glucose Range for Each CGM Glucose Range YSI (mg/dL)									
		<40	40-60	61-80	81-120	121-160	161-200	201-250	251-300	301-350	351-400
40-60											
61-80											
81-120											
121-160											
161-200											
201-250											
251-300											
301-350											
351-400											

Table 8. CGM System Accuracy by Visit Number (Sample Table)

Day Number	Number of Paired CGM-YSI	Mean Absolute Relative Difference (%)	Median Absolute Relative Difference (%)	Percent of CGM System Readings Within				
				Percent 15/15% of Reference	Percent 20/20% of Reference	Percent 30/30% of Reference	Percent 40/40% of Reference	Percent Greater than 40/40% of Reference
Day 1								
Day 7								
Day 14								
Day 30								
Day 60								
Day 90								

Table 9. CGM System between System Precision (Sample Table)

Level of Mean Glucose (mg/dL)	Mean Difference (Sensor 1 - Sensor 2) (mg/dL)	SD of Difference (mg/dL)	N Pairs
<= 70			
71-180			

Level of Mean Glucose (mg/dL)	Mean Difference (Sensor 1 - Sensor 2) (mg/dL)	SD of Difference (mg/dL)	N Pairs
> 180			
All			
PARD			
PCV			

Table 10A. CGM System Performance during Sleep Challenges (Sample Table)

Night Time (Y/N)	Number of Paired CGM-YSI	Mean Absolute Relative Difference (%)	Median Absolute Relative Difference (%)	Percent of CGM System Readings Within				
				Percent 15/15% of Reference	Percent 20/20% of Reference	Percent 30/30% of Reference	Percent 40/40% of Reference	Percent Greater than 40/40% of Reference
Y								
N								

Table 10B. CGM System between System Precision during Sleep Challenges (Sample Table)

[figure not shown]
Night Time (Y/N)	N Pairs	PARD
Y		
N		

Table 16. Effect of Gender on System and Reference Agreement (sample table)

Gender	Number of Paired Senseonics CGM and Reference	Percent within 20/20% Reference	Percent within 30/30% Reference	Percent within 40/40% Reference
M				
F				

Table 17. Effect of Age on System and Reference Agreement (sample table)

Age	Number of Paired Senseonics CGM and Reference	Percent within 20/20% Reference	Percent within 30/30% Reference	Percent within 40/40% Reference
18-20				
21-44				
45-65				
Over 65				

Table 18. Effect of BMI on System and Reference Agreement (sample table)

BMI	Number of Paired Senseonics CGM and Reference	Percent within 20/20% Reference	Percent within 30/30% Reference	Percent within 40/40% Reference
< 25				
[25, 30)				
≥ 30				

Table 19. Effect of Dominant Hand on System and Reference Agreement (sample table)

Dominant Hand (Y/N)	Number of Paired Senseonics CGM and Reference	Percent within 20/20% Reference	Percent within 30/30% Reference	Percent within 40/40% Reference
Y				
N				

Table 20. Effect of Clinical Site on System and Reference Agreement (sample table)

Site Number	Number of Paired Senseonics CGM and Reference	Percent within 20/20% Reference	Percent within 30/30% Reference	Percent within 40/40% Reference
1				
2				
3				

Table 21. Effect of Rate of Change on System and Reference Agreement (sample table)

System Rate of Change	Number of Paired Senseonics CGM and Reference	Percent within 20/20% Reference	Percent within 30/30% Reference	Percent within 40/40% Reference
<-2				
[-2,-1)				
[-1,1]				
(1,2]				
>2				

Table 22. Effect of Race or Skin Color on System and Reference Agreement (sample table)

Race and Skin Color Category	Number of Paired Senseonics CGM and Reference	Percent within 20/20% Reference	Percent within 30/30% Reference	Percent within 40/40% Reference
Race and Skin Color Category 1				
Race and Skin Color Category 2				
Race and Skin Color Category 3				

Table 23: CGM Satisfaction Survey Results (sample table)

Survey Questions	Agree Strongly (N/%)	Agree (N/%)	Neutral (N/%)	Disagree (N/%)	Disagree Strongly (N/%)
Question 1					
Question 2					
⋮					
Question N					

Table 24. Effect of Medications (sample table)

Class of Medication	Subjects Taking Medication	MARD with Medication [mean (SD) / n]	MARD with No Medication [mean (SD) / n]	P-value
Diabetes Medication				
Thyroid Medication				
Hypertension Medication				
Cholesterol Medication				

Table 25. Calibration Stability (sample table)

Time from Calibration	Number of Paired Senseonics CGM and Reference	Percent within 20/20% Reference	Percent within 30/30% Reference	Percent within 40/40% Reference
0-4 hours				
4-8 hours				
8-12 hours				

APPENDIX 2: EXAMPLE FIGURES AND TABLES OF STATISTICAL ANALYSIS RESULTS FOR THE DIFFERENT HARDWARE AND FIRMWARE COMBINATIONS

Table 2.1. Investigational Transmitter Deficiencies (Sample Table)

Type of Transmitter Deficiency	Gen 1 Tx		Gen 2 Tx	
	Number Reported	% of Total	Number Reported	% of Total
Package Label	TBD	TBD	TBD	TBD
Product Defect	TBD	TBD	TBD	TBD
Damaged Package	TBD	TBD	TBD	TBD
Product Safety	TBD	TBD	TBD	TBD
Product Performance	TBD	TBD	TBD	TBD
Other	TBD	TBD	TBD	TBD

Table 2.2. CGM System Difference to YSI within YSI Glucose Range (Sample Table)

CGM System Difference to YSI within YSI Glucose Range				
YSI Glucose Range (mg/dL)	Number of Points	Hardware Version (Firmware Version)		
		Gen 1 Tx (Study FW)	Gen 2 Tx (Study FW)	Gen 2 Tx (Updated FW)
Mean Relative Difference (%)				
Overall	TBD	TBD	TBD	TBD
<40*	TBD	TBD	TBD	TBD
40-60*	TBD	TBD	TBD	TBD
61-80*	TBD	TBD	TBD	TBD
81-180	TBD	TBD	TBD	TBD
181-300	TBD	TBD	TBD	TBD
301-350	TBD	TBD	TBD	TBD
351-400	TBD	TBD	TBD	TBD
>400	TBD	TBD	TBD	TBD
Median Relative Difference (%)				
Overall	TBD	TBD	TBD	TBD
<40*	TBD	TBD	TBD	TBD
40-60*	TBD	TBD	TBD	TBD
61-80*	TBD	TBD	TBD	TBD
81-180	TBD	TBD	TBD	TBD
181-300	TBD	TBD	TBD	TBD
301-350	TBD	TBD	TBD	TBD
351-400	TBD	TBD	TBD	TBD
>400	TBD	TBD	TBD	TBD
Mean Absolute Relative Difference (%)				
Overall	TBD	TBD	TBD	TBD
<40*	TBD	TBD	TBD	TBD
40-60*	TBD	TBD	TBD	TBD

CGM System Difference to YSI within YSI Glucose Range				
YSI Glucose Range (mg/dL)	Number of Points	Hardware Version (Firmware Version)		
		Gen 1 Tx (Study FW)	Gen 2 Tx (Study FW)	Gen 2 Tx (Updated FW)
61-80*	TBD	TBD	TBD	TBD
81-180	TBD	TBD	TBD	TBD
181-300	TBD	TBD	TBD	TBD
301-350	TBD	TBD	TBD	TBD
351-400	TBD	TBD	TBD	TBD
>400	TBD	TBD	TBD	TBD
Median Absolute Relative Difference (%)				
Overall	TBD	TBD	TBD	TBD
<40*	TBD	TBD	TBD	TBD
40-60*	TBD	TBD	TBD	TBD
61-80*	TBD	TBD	TBD	TBD
81-180	TBD	TBD	TBD	TBD
181-300	TBD	TBD	TBD	TBD
301-350	TBD	TBD	TBD	TBD
351-400	TBD	TBD	TBD	TBD
>400	TBD	TBD	TBD	TBD

*For YSI ≤80 mg/dl, the differences in mg/dl are included instead of percent difference (%).

Table 2.3. CGM System Difference to YSI within CGM System Glucose Range (Sample Table)

CGM System Difference to YSI within CGM System Glucose Range				
CGM Glucose Range (mg/dL)	Number of Points	Hardware Version (Firmware Version)		
		Gen 1 Tx (Study FW)	Gen 2 Tx (Study FW)	Gen 2 Tx (Updated FW)
Mean Relative Difference (%)				
Overall	TBD	TBD	TBD	TBD
40-60*	TBD	TBD	TBD	TBD
61-80*	TBD	TBD	TBD	TBD
81-180	TBD	TBD	TBD	TBD
181-300	TBD	TBD	TBD	TBD
301-350	TBD	TBD	TBD	TBD
351-400	TBD	TBD	TBD	TBD
Median Relative Difference (%)				
Overall	TBD	TBD	TBD	TBD
40-60*	TBD	TBD	TBD	TBD
61-80*	TBD	TBD	TBD	TBD
81-180	TBD	TBD	TBD	TBD
181-300	TBD	TBD	TBD	TBD
301-350	TBD	TBD	TBD	TBD
351-400	TBD	TBD	TBD	TBD

CGM System Difference to YSI within CGM System Glucose Range				
CGM Glucose Range (mg/dL)	Number of Points	Hardware Version (Firmware Version)		
		Gen 1 Tx (Study FW)	Gen 2 Tx (Study FW)	Gen 2 Tx (Updated FW)
Mean Absolute Relative Difference (%)				
Overall	TBD	TBD	TBD	TBD
40-60*	TBD	TBD	TBD	TBD
61-80*	TBD	TBD	TBD	TBD
81-180	TBD	TBD	TBD	TBD
181-300	TBD	TBD	TBD	TBD
301-350	TBD	TBD	TBD	TBD
351-400	TBD	TBD	TBD	TBD
Median Absolute Relative Difference (%)				
Overall	TBD	TBD	TBD	TBD
40-60*	TBD	TBD	TBD	TBD
61-80*	TBD	TBD	TBD	TBD
81-180	TBD	TBD	TBD	TBD
181-300	TBD	TBD	TBD	TBD
301-350	TBD	TBD	TBD	TBD
351-400	TBD	TBD	TBD	TBD

*For CGM \leq 80 mg/dL, the differences in mg/dL are included instead of percent difference (%).

Table 2.4. CGM System Agreement to Reference within YSI Glucose Ranges (Sample Table)

Percent of CGM System Readings Agreement By YSI Range				
YSI Glucose Range (mg/dL)	Number of Points	Hardware Version (Firmware Version)		
		Gen 1 Tx (Study FW)	Gen 2 Tx (Study FW)	Gen 2 Tx (Updated FW)
Within 15/15%				
Overall	TBD	TBD	TBD	TBD
<40	TBD	TBD	TBD	TBD
40-60	TBD	TBD	TBD	TBD
61-80	TBD	TBD	TBD	TBD
81-180	TBD	TBD	TBD	TBD
181-300	TBD	TBD	TBD	TBD
301-350	TBD	TBD	TBD	TBD
351-400	TBD	TBD	TBD	TBD
>400	TBD	TBD	TBD	TBD
Within 20/20%				
Overall				
<40	TBD	TBD	TBD	TBD
40-60	TBD	TBD	TBD	TBD
61-80	TBD	TBD	TBD	TBD
81-180	TBD	TBD	TBD	TBD
181-300	TBD	TBD	TBD	TBD

Percent of CGM System Readings Agreement By YSI Range				
YSI Glucose Range (mg/dL)	Number of Points	Hardware Version (Firmware Version)		
		Gen 1 Tx (Study FW)	Gen 2 Tx (Study FW)	Gen 2 Tx (Updated FW)
301-350	TBD	TBD	TBD	TBD
351-400	TBD	TBD	TBD	TBD
>400	TBD	TBD	TBD	TBD
Within 30/30%				
Overall	TBD	TBD	TBD	TBD
<40	TBD	TBD	TBD	TBD
40-60	TBD	TBD	TBD	TBD
61-80	TBD	TBD	TBD	TBD
81-180	TBD	TBD	TBD	TBD
181-300	TBD	TBD	TBD	TBD
301-350	TBD	TBD	TBD	TBD
351-400	TBD	TBD	TBD	TBD
>400	TBD	TBD	TBD	TBD
Within 40/40%				
Overall	TBD	TBD	TBD	TBD
<40	TBD	TBD	TBD	TBD
40-60	TBD	TBD	TBD	TBD
61-80	TBD	TBD	TBD	TBD
81-180	TBD	TBD	TBD	TBD
181-300	TBD	TBD	TBD	TBD
301-350	TBD	TBD	TBD	TBD
351-400	TBD	TBD	TBD	TBD
>400	TBD	TBD	TBD	TBD

Table 2.5. CGM System Agreement to Reference within CGM System Glucose Ranges (Sample Table)

Percent of CGM System Readings Agreement By CGM Range				
CGM Glucose Range (mg/dL)	Number of Points	Hardware Version (Firmware Version)		
		Gen 1 Tx (Study FW)	Gen 2 Tx (Study FW)	Gen 2 Tx (Updated FW)
Within 15/15%				
Overall	TBD	TBD	TBD	TBD
40-60	TBD	TBD	TBD	TBD
61-80	TBD	TBD	TBD	TBD
81-180	TBD	TBD	TBD	TBD
181-300	TBD	TBD	TBD	TBD
301-350	TBD	TBD	TBD	TBD
351-400	TBD	TBD	TBD	TBD
Within 20/20%				
Overall	TBD	TBD	TBD	TBD
40-60	TBD	TBD	TBD	TBD

Percent of CGM System Readings Agreement By CGM Range				
CGM Glucose Range (mg/dL)	Number of Points	Hardware Version (Firmware Version)		
		Gen 1 Tx (Study FW)	Gen 2 Tx (Study FW)	Gen 2 Tx (Updated FW)
61-80	TBD	TBD	TBD	TBD
81-180	TBD	TBD	TBD	TBD
181-300	TBD	TBD	TBD	TBD
301-350	TBD	TBD	TBD	TBD
351-400	TBD	TBD	TBD	TBD
Within 30/30%				
Overall	TBD	TBD	TBD	TBD
40-60	TBD	TBD	TBD	TBD
61-80	TBD	TBD	TBD	TBD
81-180	TBD	TBD	TBD	TBD
181-300	TBD	TBD	TBD	TBD
301-350	TBD	TBD	TBD	TBD
351-400	TBD	TBD	TBD	TBD
Within 40/40%				
Overall	TBD	TBD	TBD	TBD
40-60	TBD	TBD	TBD	TBD
61-80	TBD	TBD	TBD	TBD
81-180	TBD	TBD	TBD	TBD
181-300	TBD	TBD	TBD	TBD
301-350	TBD	TBD	TBD	TBD
351-400	TBD	TBD	TBD	TBD

Table 2.6. Concurrence of CGM System Readings and YSI Values within YSI Glucose Ranges (Sample Table)
Table 2.6A

YSI (mg/dL)	Number of Paired CGM-YSI (n)	Gen 1 Tx (Study FW)								
		Percent of Matched Pairs in Each CGM System Glucose Range for Each YSI Glucose Range								
		CGM (mg/dL)	40-60	61-80	81-120	121-160	161-200	201-250	251-300	301-350
<40										
40-60										
61-80										
81-120										
121-160										
161-200										
201-250										
251-300										
301-350										
351-400										
>400										

Table 2.6B

YSI (mg/dL)	Number of Paired CGM-YSI (n)	Gen 2 Tx (Study FW) Percent of Matched Pairs in Each CGM System Glucose Range for Each YSI Glucose Range CGM (mg/dL)								
		40-60	61-80	81-120	121- 160	161- 200	201- 250	251- 300	301- 350	351-400
<40										
40-60										
61-80										
81-120										
121-160										
161-200										
201-250										
251-300										
301-350										
351-400										
>400										

Table 2.6C

YSI (mg/dL)	Number of Paired CGM-YSI (n)	Gen 2 Tx (Updated FW) Percent of Matched Pairs in Each CGM System Glucose Range for Each YSI Glucose Range CGM (mg/dL)								
		40-60	61-80	81-120	121- 160	161- 200	201- 250	251- 300	301- 350	351-400
<40										
40-60										
61-80										
81-120										
121-160										
161-200										
201-250										
251-300										
301-350										
351-400										
>400										

Table 2.7. Concurrence of CGM System Readings and YSI Values within CGM System Ranges (Sample Table)
Table 2.7A

CGM (mg/dL)	Number of Paired CGM-YSI (n)	Gen 1 Tx (Study FW) Percent of Matched Pairs in Each YSI Glucose Range for Each CGM Glucose Range YSI (mg/dL)									
		<40	40-60	61-80	81-120	121- 160	161- 200	201- 250	251- 300	301- 350	351- 400
40-60											
61-80											
81-120											
121-160											

CGM (mg/dL)	Number of Paired CGM-YSI (n)	Gen 1 Tx (Study FW)									
		<40	40-60	61-80	81-120	121- 160	161- 200	201- 250	251- 300	301- 350	351- 400
161-200											
201-250											
251-300											
301-350											
351-400											

Table 2.7B

CGM (mg/dL)	Number of Paired CGM-YSI (n)	Gen 2 Tx (Study FW)									
		<40	40-60	61-80	81-120	121- 160	161- 200	201- 250	251- 300	301- 350	351- 400
40-60											
61-80											
81-120											
121-160											
161-200											
201-250											
251-300											
301-350											
351-400											

Table 2.7C

CGM (mg/dL)	Number of Paired CGM-YSI (n)	Gen 2 Tx (Updated FW)									
		<40	40-60	61-80	81-120	121- 160	161- 200	201- 250	251- 300	301- 350	351- 400
40-60											
61-80											
81-120											
121-160											
161-200											
201-250											
251-300											
301-350											
351-400											

Table 2.8. CGM System Accuracy by Visit Number (Sample Table)
Table 2.8A

Percent of CGM System Readings within 15/15%				
YSI Glucose Range (mg/dL)	Number of Points	Hardware Version (Firmware Version)		
		Gen 1 Tx (Study FW)	Gen 2 Tx (Study FW)	Gen 2 Tx (Updated FW)
Day 1				

Overall				
<40	TBD	TBD	TBD	TBD
40-60	TBD	TBD	TBD	TBD
61-80	TBD	TBD	TBD	TBD
81-180	TBD	TBD	TBD	TBD
181-300	TBD	TBD	TBD	TBD
301-350	TBD	TBD	TBD	TBD
351-400	TBD	TBD	TBD	TBD
>400	TBD	TBD	TBD	TBD

Day 7

Overall				
<40	TBD	TBD	TBD	TBD
40-60	TBD	TBD	TBD	TBD
61-80	TBD	TBD	TBD	TBD
81-180	TBD	TBD	TBD	TBD
181-300	TBD	TBD	TBD	TBD
301-350	TBD	TBD	TBD	TBD
351-400	TBD	TBD	TBD	TBD
>400	TBD	TBD	TBD	TBD

Day 14

Overall				
<40	TBD	TBD	TBD	TBD
40-60	TBD	TBD	TBD	TBD
61-80	TBD	TBD	TBD	TBD
81-180	TBD	TBD	TBD	TBD
181-300	TBD	TBD	TBD	TBD
301-350	TBD	TBD	TBD	TBD
351-400	TBD	TBD	TBD	TBD
>400	TBD	TBD	TBD	TBD

Day 30

Overall				
<40	TBD	TBD	TBD	TBD
40-60	TBD	TBD	TBD	TBD
61-80	TBD	TBD	TBD	TBD
81-180	TBD	TBD	TBD	TBD
181-300	TBD	TBD	TBD	TBD
301-350	TBD	TBD	TBD	TBD
351-400	TBD	TBD	TBD	TBD
>400	TBD	TBD	TBD	TBD

Table 2.8B

Percent of CGM System Readings within 20/20%				
YSI Glucose Range (mg/dL)	Number of Points	Hardware Version (Firmware Version)		
		Gen 1 Tx (Study FW)	Gen 2 Tx (Study FW)	Gen 2 Tx (Updated FW)
Day 1				
Overall				
<40	TBD	TBD	TBD	TBD
40-60	TBD	TBD	TBD	TBD
61-80	TBD	TBD	TBD	TBD
81-180	TBD	TBD	TBD	TBD
181-300	TBD	TBD	TBD	TBD
301-350	TBD	TBD	TBD	TBD
351-400	TBD	TBD	TBD	TBD
>400	TBD	TBD	TBD	TBD
Day 7				
Overall				
<40	TBD	TBD	TBD	TBD
40-60	TBD	TBD	TBD	TBD
61-80	TBD	TBD	TBD	TBD
81-180	TBD	TBD	TBD	TBD
181-300	TBD	TBD	TBD	TBD
301-350	TBD	TBD	TBD	TBD
351-400	TBD	TBD	TBD	TBD
>400	TBD	TBD	TBD	TBD
Day 14				
Overall				
<40	TBD	TBD	TBD	TBD
40-60	TBD	TBD	TBD	TBD
61-80	TBD	TBD	TBD	TBD
81-180	TBD	TBD	TBD	TBD
181-300	TBD	TBD	TBD	TBD
301-350	TBD	TBD	TBD	TBD
351-400	TBD	TBD	TBD	TBD
>400	TBD	TBD	TBD	TBD
Day 30				
Overall				
<40	TBD	TBD	TBD	TBD
40-60	TBD	TBD	TBD	TBD
61-80	TBD	TBD	TBD	TBD
81-180	TBD	TBD	TBD	TBD
181-300	TBD	TBD	TBD	TBD
301-350	TBD	TBD	TBD	TBD
351-400	TBD	TBD	TBD	TBD
>400	TBD	TBD	TBD	TBD

Table 2.8C

Percent of CGM System Readings within 30/30%				
YSI Glucose Range (mg/dL)	Number of Points	Hardware Version (Firmware Version)		
		Gen 1 Tx (Study FW)	Gen 2 Tx (Study FW)	Gen 2 Tx (Updated FW)
Day 1				
Overall				
<40	TBD	TBD	TBD	TBD
40-60	TBD	TBD	TBD	TBD
61-80	TBD	TBD	TBD	TBD
81-180	TBD	TBD	TBD	TBD
181-300	TBD	TBD	TBD	TBD
301-350	TBD	TBD	TBD	TBD
351-400	TBD	TBD	TBD	TBD
>400	TBD	TBD	TBD	TBD
Day 7				
Overall				
<40	TBD	TBD	TBD	TBD
40-60	TBD	TBD	TBD	TBD
61-80	TBD	TBD	TBD	TBD
81-180	TBD	TBD	TBD	TBD
181-300	TBD	TBD	TBD	TBD
301-350	TBD	TBD	TBD	TBD
351-400	TBD	TBD	TBD	TBD
>400	TBD	TBD	TBD	TBD
Day 14				
Overall				
<40	TBD	TBD	TBD	TBD
40-60	TBD	TBD	TBD	TBD
61-80	TBD	TBD	TBD	TBD
81-180	TBD	TBD	TBD	TBD
181-300	TBD	TBD	TBD	TBD
301-350	TBD	TBD	TBD	TBD
351-400	TBD	TBD	TBD	TBD
>400	TBD	TBD	TBD	TBD
Day 30				
Overall				
<40	TBD	TBD	TBD	TBD
40-60	TBD	TBD	TBD	TBD
61-80	TBD	TBD	TBD	TBD
81-180	TBD	TBD	TBD	TBD
181-300	TBD	TBD	TBD	TBD
301-350	TBD	TBD	TBD	TBD
351-400	TBD	TBD	TBD	TBD
>400	TBD	TBD	TBD	TBD

Table 2.8D

Percent of CGM System Readings within 40/40%				
YSI Glucose Range (mg/dL)	Number of Points	Hardware Version (Firmware Version)		
		Gen 1 Tx (Study FW)	Gen 2 Tx (Study FW)	Gen 2 Tx (Updated FW)
Day 1				
Overall				
<40	TBD	TBD	TBD	TBD
40-60	TBD	TBD	TBD	TBD
61-80	TBD	TBD	TBD	TBD
81-180	TBD	TBD	TBD	TBD
181-300	TBD	TBD	TBD	TBD
301-350	TBD	TBD	TBD	TBD
351-400	TBD	TBD	TBD	TBD
>400	TBD	TBD	TBD	TBD
Day 7				
Overall				
<40	TBD	TBD	TBD	TBD
40-60	TBD	TBD	TBD	TBD
61-80	TBD	TBD	TBD	TBD
81-180	TBD	TBD	TBD	TBD
181-300	TBD	TBD	TBD	TBD
301-350	TBD	TBD	TBD	TBD
351-400	TBD	TBD	TBD	TBD
>400	TBD	TBD	TBD	TBD
Day 14				
Overall				
<40	TBD	TBD	TBD	TBD
40-60	TBD	TBD	TBD	TBD
61-80	TBD	TBD	TBD	TBD
81-180	TBD	TBD	TBD	TBD
181-300	TBD	TBD	TBD	TBD
301-350	TBD	TBD	TBD	TBD
351-400	TBD	TBD	TBD	TBD
>400	TBD	TBD	TBD	TBD
Day 30				
Overall				
<40	TBD	TBD	TBD	TBD
40-60	TBD	TBD	TBD	TBD
61-80	TBD	TBD	TBD	TBD
81-180	TBD	TBD	TBD	TBD
181-300	TBD	TBD	TBD	TBD
301-350	TBD	TBD	TBD	TBD
351-400	TBD	TBD	TBD	TBD
>400	TBD	TBD	TBD	TBD

Table 2.9. System Reliability

System Reliability	Transmitter Version	
	Gen 1 Tx (Study FW)	Gen 2 Tx (Study FW)
Matched CGM-YSI Pairs	TBD*	TBD *
Number of Sensors Logging Data with Transmitter	TBD	TBD
Mean Number of Matched Pairs Per Sensor	TBD	TBD

* Does not include data when the Systems displays High or Low Glucose

Table 2.10. CGM System Performance during Sleep Challenges (Sample Table)

During Night	Hardware Version (Firmware Version)			During Day	Hardware Version (Firmware Version)		
	Gen 1 Tx (Study FW)	Gen 2 Tx (Study FW)	Gen 2 Tx (Updated FW)		Gen 1 Tx (Study FW)	Gen 2 Tx (Study FW)	Gen 2 Tx (Updated FW)
Mean Absolute Relative Difference (%)	TBD	TBD	TBD	Mean Absolute Relative Difference (%)	TBD	TBD	TBD
Median Absolute Relative Difference (%)	TBD	TBD	TBD	Median Absolute Relative Difference (%)	TBD	TBD	TBD
15/15%				15/15%			
20/20%				20/20%			
30/30%				30/30%			
40/40%				40/40%			

Table 2.11. CGM System between System Precision during Sleep Challenges (Sample Table)

Night Time (Y/N)	N Pairs	Gen 1 Tx (Study FW) PARD	Gen 2 Tx (Study FW) PARD	Gen 2 Tx (Updated FW) PARD
Y				
N

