4.5.16 Sleep Assessment

Designated subjects will be inserted with two sensors, one in each upper arm. Each subject will spend two overnights in the clinic where they will be instructed to sleep on one side for situations in which compression of the sensor site may occur during sleep. "Sensor drop-out," if a phenomenon of the Senseonics CGM System, will be identified during these periods. Sleep position will not be documented.

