11.3.2.2 Sample Size and Power Calculation

This study does not feature any inferential statistics. The sample size for the study was not determined based on a power calculation. Instead, the sample size of 36 subjects with sensors inserted was selected based on the objectives of the study and was mutually agreed upon between the Sponsor and the FDA.

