3 STUDY DESIGN

This is a non-randomized, prospective, single-arm, multi-center study, whereby approximately 44 subjects will be enrolled and 36 subjects will be inserted in the United States at up to 4 sites. The investigation will include both clinic visits and home use of the Senseonics CGM System. The subjects will have one or two Sensors inserted by trained Investigators. The Sensors will be inserted in the upper arms of the subjects. The accuracy of the Senseonics CGM System will be evaluated during clinic visits comparing Sensor glucose values and plasma glucose values measured on a bedside glucose analyzer. For qualifying subjects, during the clinic visits, there will be planned hyperglycemia and hypoglycemia challenges. Effects of compression/sensor dropout will be evaluated during the designated overnight periods.

In this study, including the clinic and home settings, all diabetes care decisions will be based on SMBG blood glucose values and clinical standard of care, rather than Senseonics CGM System results.

This study will not be randomized. Subjects will be selected consecutively (i.e., selecting every subject in the order they present at the site) among those who meet the

inclusion/exclusion criteria.

The Subject visit schedule includes 9 visits over a period of approximately 4.5 months (inclusive of visit windows from screening visit through follow-up visit). A subset of a minimum of 6 and a maximum of 9 subjects will have blood samples drawn daily for the first 7 days of sensor wear for additional dexamethasone screening and to determine blood draw time points during the first week of sensor wear for the remaining subjects. These subjects will only have one sensor inserted in the left arm, which will be linked to the Gen 1 transmitter. Remaining subjects will have 2 sensors inserted, one in each arm, with the left sensor linked to a Gen 1 transmitter, and the right sensor linked to the Gen 2 transmitter. These subjects may be required to make additional visits for dexamethasone screening between visits 3 and 4.

The study is anticipated to take approximately 6 months, including the enrollment period.

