6.4 Analysis Populations

Effectiveness Analysis population: The effectiveness analysis and exploratory effectiveness endpoints will be based on all data from all subjects in this investigation with at least one paired glucose reading (one Sensor with one reference glucose). The Senseonics CGM System and reference readings are compared by pairing each reference reading with the first Sensor reading that occurred up to 5 minutes after sample acquisition.

Safety Analysis Population: Safety analysis will be based on all subjects that undergo the sensor insertion in this investigation.

Dexamethasone Analysis Population: The approximately 6 to 9 subjects with Sensor's inserted will constitute the dexamethasone analysis population to determine if and when a peak dexamethasone level occurs. Subsequent to determining if and when a peak occurs, all subjects with Sensor's inserted will constitute the complete dexamethasone analysis population.

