6.10.1.7 Effect of compression on sensor performance during sleep challenges

For the sleep assessment periods during visits 4 & 5, compression may occur to the sensor site when the subject is sleeping at night. The system's difference and agreement with reference and between system precision will be compared between the night time and the day time (Tables 10A and 10B in APPENDIX 1).

6.10.1.8 Mean Absolute Difference between sensor and reference measurements for reference values less than or equal to 80mg/dL

The mean absolute difference (MAD) for reference glucose values less than or equal to 80 mg/dL is defined as the absolute difference of paired Senseonics CGM System and Reference readings for reference glucose values ≤ 80 mg/dL.

$$MAD = \left(\sum |(Glucose)_{SENSOR} - (Glucose)_{REFERENCE}| \right) / n$$

This analysis will quantify both cumulative results as well as stability over time in 30 day intervals (Tables 11A and 11B in APPENDIX 1).

6.10.1.9 Mean Absolute Difference between sensor and reference measurements for system full scale range (40-400mg/dL)

$$MAD = \left(\sum |(Glucose)_{SENSOR} - (Glucose)_{REFERENCE}| \right) / n$$

This analysis will quantify both cumulative results as well as stability over time in 30 day intervals (Tables 11A and 11B in APPENDIX 1).

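### Overnight drop-out is a stated question, but the planned tables cannot measure it if it takes the form of lost readings, and the reliability table has no draws-taken or sensors-inserted base

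*SAP*

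**What the plan says.** **The question.** SAP section 3, like Protocol 3.3.1, states: "Effects of compression/sensor dropout will be evaluated during the designated overnight periods". Protocol 4.5.16 adds that drop-out, "if a phenomenon of the Senseonics CGM System, will be identified during these periods". Neither document defines the term.

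**The assigned analysis.** SAP 6.10.1.7 gives one analysis: "The system's difference and agreement with reference and between system precision will be compared between the night time and the day time". Its outputs are Tables 10A and 10B, with Tables 2.10 and 2.11 as the versions by hardware and firmware configuration. They contain MARD, median ARD, agreement and PARD. Tables 10A, 10B and 2.11 also print the number of pairs; Table 2.10 does not.

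**How a pair arises.** SAP 6.4 compares system and reference by "pairing each reference reading with the first Sensor reading that occurred up to 5 minutes after sample acquisition". A draw with no such reading makes no pair. The effectiveness population is subjects "with at least one paired glucose reading (one Sensor with one reference glucose").

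**Reliability.** SAP Appendix 2, Table 2.9 has three rows: matched pairs, "Number of Sensors Logging Data with Transmitter" and "Mean Number of Matched Pairs Per Sensor". A footnote leaves out High and Low displays. The columns are Gen 1 and Gen 2 with study firmware. The third configuration named in SAP 4.2.1, Gen 2 with updated firmware, has no column.

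**The concern.** The system can be silent by design. Protocol 1.1.2 says glucose is not calculated after an unsuccessful calibration or more than 24 hours without the transmitter, and SAP 6.2 says readings stop at end of life. Downloads that cannot be used are treated as missing data (Protocol 10.2.2). Draws missed through lost IV access or analyzer failure are not protocol deviations (Protocol 5.9.2), so a deviation listing need not supply them.

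A fall in the number of pairs therefore has at least two sources: the reference draw was not taken, or it was taken and the sensor gave nothing. The planned tables do not separate them. If readings are lost mainly when the signal is poor, accuracy is computed on the better moments and the loss itself is not reported as a rate. For a study that names drop-out as something to evaluate, that leaves one plausible form of it without a measure.

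**Working it through.** No alpha or power calculation is involved: the study is descriptive, and Protocol 11.3.2.2 says "The sample size for the study was not determined based on a power calculation". The check is on counts.

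**1. The plan's own figure.** Protocol 11.1.4 expects 22,786 pairs from 66 sensors. The nine range totals sum to 22,787, and the session columns give 3 × (4,632 + 2,965) = 22,791, so the figure reproduces to rounding. The 66 sensors are 6 × 1 + 30 × 2; with 9 single-sensor subjects there would be 9 + 27 × 2 = 63.

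**2. Opportunities for a pair.** The schedule of events gives about 89 draws at each of Visits 3 to 5 and about 59 at each of Visits 6 to 8. These assume 3 hours and 1 hour of 5-minute sampling.
- With that sampling: 66 × 3 × (89 + 59) = 29,304, and 22,786 / 29,304 = 77.8%, a gap of 6,518 (22%).
- With 15-minute sampling throughout: 66 × 3 × (16 × 4 + 12.5 × 4) = 66 × 3 × 114 = 22,572, slightly below 22,786, so no gap.

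The expected yield of pairs per draw thus depends on how much 5-minute sampling takes place. Without a count of draws actually taken, the final pair count cannot be interpreted either.

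**3. Sleep nights, drop-out as lost readings.** The overnight period in Protocol 4.5 runs from about 0:00 to 07:00. At 15-minute sampling that is 7 × 4 = 28 draws a night. Two nights and 30 two-sensor subjects give 28 × 2 × 60 = 3,360 possible night pairs. Assumed losses per sensor per night:

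| Hours lost | Share of night pairs lost |
|---|---|
| 0.5 | 2/28 = 7% |
| 1 | 4/28 = 14% |
| 2 | 8/28 = 29% |
| 3 | 12/28 = 43% |

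MARD and agreement are computed on what remains. PARD needs both sensors: independent loss of 5%, 10% or 20% per sensor removes 1 − (1 − p)² = 9.8%, 19% or 36% of its pairs. The only trace is a smaller N.

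**4. Sleep nights, drop-out as false readings.** Assume a base MARD of 9% and a 40% error in a share p of night pairs. Night MARD is 9(1 − p) + 40p, which is 10.6%, 12.1% or 15.2% for p = 5%, 10% or 20%. Tables 10A and 2.10 would show this.

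**5. Table 2.9.** Assume 22,786 / 66 = 345.2 pairs per logging sensor and 30 inserted Gen 2 sensors, of which k log nothing.

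| k | Mean per logging sensor | Mean per inserted sensor |
|---|---|---|
| 0 | 345.2 | 345.2 |
| 1 | 345.2 | 333.7 |
| 3 | 345.2 | 310.7 |
| 6 | 345.2 | 276.2 |

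The table does not say which divisor it uses. Logging sensors is the natural reading, because that is the only sensor count printed.

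**The case against.** A reader might infer that drop-out cannot appear in the results at all. The documents do not support that. Compression and drop-out are treated as one topic, false readings would enter the night and day comparison (step 4), and Tables 10A, 10B and 2.11 print pair counts that lost readings would lower. What stands is that those counts have no denominator.

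A reader might also infer that no output registers silence. SAP 6.10.1.16 defines a missed event detection rate on reference values past the alert setting where the device did not alert, so in Tables 14A and 14B a silent device could count as a miss. But this covers only glucose past an alert setting and mixes silence with inaccurate readings, and the SAP does not say whether draws without a sensor value are kept. Kaplan-Meier counts only retirement alerts, and the deficiency tables count only what is reported.

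On Gen 1 against Gen 2, subjects with two sensors wear both transmitters at the same visits, so a missed draw is lost to both arms and the comparison is partly protected. The 6 to 9 single-sensor subjects, and the move of the Gen 1 transmitter to the other arm after a suspected primary failure (Protocol 5.10), blur that protection but do not remove it. Partial loss would lower mean pairs per sensor, and the printed number of logging sensors can be set against planned insertions by hand.

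Finally, the study is descriptive, the timestamps are kept, and SAP section 1 refers data processing to PLN-0079, which may cover unmatched readings. The opening tables of Appendix 1 were not in the copy I had, but the SAP text that introduces them describes no capture table. A rate can indeed be computed later; the case for specifying it now is that the study has already said it will evaluate drop-out.

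**Conclusion.** The concern holds in a limited form. If drop-out means lost readings, the plan as written can neither quantify it nor separate it from missed reference draws, and Table 2.9 lacks the bases a reliability measure needs. If drop-out means false readings, the planned tables would show it. No planned estimate is made wrong as a calculation on existing pairs.

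A reader might take 29,304 against 22,786 to mean that the plan expects to lose 22% of opportunities. It does not say so. The draw counts are approximate and include 5-minute sampling that not every subject will reach, the expected-pairs table covers only 40 to 400 mg/dL, and under 15-minute sampling the gap disappears.

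The other sizes are illustrations resting on assumptions: 14% of night pairs for one lost hour (7% to 43% for half an hour to three hours), and 345.2 against 310.7 pairs per sensor if 3 of 30 Gen 2 sensors log nothing and the divisor is logging sensors.

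**What to change.** - Define drop-out in the SAP, saying whether it covers missing values, false values or both.
- In Tables 2.9, 8, 10A and 2.10, by configuration (and by night and day in the sleep tables), report the YSI draws taken while a sensor was inserted and assigned a transmitter, and the percent with a sensor value within 5 minutes. Count High and Low displays separately.
- In Table 2.9, use all inserted sensors as the base, including those with zero pairs, state the divisor, and add the updated-firmware column.
- For the sleep nights, also report expected and missing 5-minute sensor readings by night and day.

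The cost is a few table columns. Sensor readings already carry timestamps (Protocol 10.2.1) and the reference records are kept (Protocol 10.2.3), so no new data are needed.
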